5.2. Primary Efficacy Endpoint

5.2.1. Primary Estimand and Analysis Set

Given that all analyses are exploratory due to the reduced sample size, no primary estimand is specified.

The primary analysis will be based on the ITT analysis set (see Section 2.6.1.1). The ITT analysis set includes all randomized subjects. The analysis of the PACC change score will only include subjects for whom the PACC change score is non-missing at ≥ 1 post-baseline time point.

Measurements collected after initiation of any Alzheimer adjunctive therapy will be included in the analysis. Measurements collected after treatment discontinuation will not be included in the analysis in the on-treatment analysis.

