**End of Treatment or Early Withdrawal**

Every attempt should be made to follow subjects through their final visit of the double-blind treatment phase (Month 54). If a subject discontinues the study prematurely for any reason, he/she will be expected to complete the Early Termination (ET) visit. Subjects who discontinue study medication prematurely but do not withdraw from the study will be asked to complete all regular study visits through the end of the study. To reduce burden on subjects and increase compliance, the focus will be on collecting primary and secondary clinical outcome measures and reducing other assessments in these subjects.

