## 11.3. Efficacy Analyses

### 11.3.1. Analysis of the Primary Endpoint

The primary objective of this study is to test the hypothesis that either dose regimen evaluated for atabecestat will slow cognitive decline compared with placebo, as measured by the primary endpoint of the PACC change from baseline at Month 54 (see Section 9.3.1).

The primary estimand, the main clinical quantity of interest to be estimated in the study, is defined by the difference in means versus placebo for the primary endpoint in the specified population under the following postrandomization measure of intervention:

- **Population:** amyloid-positive subjects who are asymptomatic at risk for developing Alzheimer's dementia
- **Endpoint:** The Month 54 (Year 4.5) PACC change score (as defined in Section 9.3.1)
- **Measure of Intervention:** the effect of the initially randomized treatment regardless of treatment compliance or initiation of any Alzheimer adjunctive therapy.

The primary analysis will be based on the intent-to-treat analysis set, which includes all randomized subjects. The analysis of the PACC change score will only include subjects for whom the PACC change score is non-missing at least 1 postbaseline time point. Measurements collected after initiation of any Alzheimer adjunctive therapy will be included in the analysis for the primary estimand. Measurements collected after treatment discontinuations due to reasons potentially related to treatment (eg, treatment-related adverse events or lack of efficacy) will also be included in the analysis of the primary estimand. However, measurements collected after treatment discontinuations due to events that are clearly not treatment-related (eg, life events such as relocation, loss of transportation, loss of informant) will not be included in the analysis of the primary estimand.

A mixed effect model for repeated measurement (MMRM) analysis will be performed to assess the treatment effect. The change from baseline in PACC at each visit that the endpoint is measured will be the dependent variable. Visits scheduled for the measure will be treated as a categorical variable with values equal to the visit numbers. An unstructured covariance structure will be assumed. The model for the fixed effects will include the following terms: baseline of the endpoint measure, treatment group, visit, treatment-by-visit interaction, age, sex, education, hippocampal volume, country, and *APOE*  $\epsilon 4$  carrier status.

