2.3. Reference Start Date and Analysis Phases

The analysis reference start date (Study Day 1) is defined as the date of the first dose of study medication. The Study Day of an event start or stop date is defined relative to the analysis reference start date as:

- Event date – analysis reference start date + 1, if the visit/event date is on or after the analysis reference start date, or

- Event date – analysis reference start date -1, if the visit/event date is before the analysis reference start date

Study Days <1 will be considered in the Screening analysis phase; Study Days \geq 1 (there is no Study Day 0) will be considered in the Double-blind analysis phase.

For visit dates prior to, or on, the date of the last dose of study medication, an Analysis Day will be defined as above relative to the analysis reference start date. For visit dates after the treatment end date, an Analysis Day is defined relative to the treatment end date as: Visit date – treatment end date + 1.

- Analysis reference start date (date of first dose as above) for all timepoints after first dose (whether before or after last dose)
- For assessments after last dose, use last observation before last dose as the reference time point.

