5. EFFICACY

Inferential analyses or descriptive analyses will be performed for the on-treatment period. For off-treatment period, only descriptive statistics will be presented.

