5.2.3. Analysis Methods

The primary analysis is based on the primary analysis set defined in Section 5.2.1 and uses an MMRM model. This relies on the Missing at Random (MAR) assumption: after accounting in the model for the effects of the covariates and for the available efficacy scores, the unobserved data have the same distribution as the observed data.

The PACC change score will be analyzed by an MMRM model based on observed data at on-treatment visits. The fixed terms for this model are treatment group, sex, country, APOE ε4 carrier status, education level, PACC baseline score, age at study entry, average hippocampal volume at baseline, time point (as a factor), and the interaction of treatment and time point. Subject is included as a random effect.

Comparisons between each atabecestat dose group and placebo will be performed at Months 6, 12, and 18 by using the appropriate contrasts based on this model. The Kenward-Roger approximation will be used to estimate the denominator degrees of freedom. Between-treatment differences in LS Means with the corresponding 95% confidence intervals (CIs) and p-values will be provided. If the unstructured covariance matrix results in a lack of convergence, starting values will be supplied using estimates from simpler structures. If this strategy does not result in

convergence then the following structures will be used in sequence: heterogeneous autoregressive of order 1 (ARH(1)), heterogeneous compound symmetry (CSH), and homogeneous compound symmetry (CS).

Plots of mean (\pm SE) PACC change score over time by treatment group will be provided for observed data and for estimates based on the MMRM.

For the off-treatment period, change of PACC and the components from off-treatment baseline will be summarized.

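### The only inferential PACC composite model uses on-treatment visits alone; a second model keeping scores collected after individual discontinuation, up to 17 May 2018, would be a cheap improvement

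*SAP*

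**What the plan says.** **SAP.** Section 5.2.1 fixes the set of subjects: "The primary analysis will be based on the ITT analysis set (see Section 2.6.1.1"; Section 2.6.1.1 defines that set as all randomized subjects. Section 5.2.1 then limits the scores: "Measurements collected after treatment discontinuation will not be included in the analysis in the on-treatment analysis". No distinction is made by reason for stopping, or between an individual's stop and the sponsor-wide stop. Section 5.2.3 repeats the limit: "The PACC change score will be analyzed by an MMRM model based on observed data at on-treatment visits". Section 5 adds: "For off-treatment period, only descriptive statistics will be presented". Section 5.2.1 also states that all analyses are exploratory and that no primary estimand is specified.

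**Protocol.** Section 11.3.1 targets "the effect of the initially randomized treatment regardless of treatment compliance". It continues: "Measurements collected after treatment discontinuations due to reasons potentially related to treatment (eg, treatment-related adverse events or lack of efficacy) will also be included". Only scores after clearly unrelated stops, such as relocation, are to be left out. Section 11.3.4 says follow-up data from subjects who stop drug early will be used in sensitivity analyses. The scores are meant to exist: "Subjects who discontinue study medication prematurely but do not withdraw from the study will be asked to complete all regular study visits" (Synopsis, End of Treatment or Early Withdrawal; Section 10.2 says the same).

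**The concern.** The subjects are defined by randomization, but the scores that enter the model are defined by staying on drug. Some stopping is plausibly related to arm. Protocol 10.2 makes discontinuation mandatory at given liver-enzyme levels, and Section 12.3.4 lists raised liver enzymes as an identified adverse drug reaction. If active and placebo subjects leave the data at different rates and for different reasons, the Month 6, 12 and 18 contrasts no longer compare the groups as randomized.

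The early cessation is a good reason to set aside scores after 17 May 2018, because that stop applied to everyone still on drug. It is not a reason to set aside scores from subjects who stopped individually before that date and kept attending visits. At stake is whether the report contains one PACC comparison of the kind the protocol intended, alongside the on-drug comparison.

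**Working it through.** No figure in the plan is disputed here. The check is mainly a comparison of rules, followed by an illustration of scale.

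**1. The SAP's own counts reproduce.** 557/1650 = 33.8% (stated 34%). 447/557 = 80.3% with 12 months of treatment or less (stated 80%). Neither document gives discontinuations by arm.

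**2. Which scores enter.**

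| Scores collected after | Protocol 11.3.1 | SAP 5.2.1 and 5.2.3 |
|---|---|---|
| a potentially treatment-related stop | included | excluded |
| a clearly unrelated stop | excluded | excluded |
| start of Alzheimer adjunctive therapy | included | included |

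The conflict is confined to the first row.

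**3. A subject who stops early.** Take a last dose on Day 80.
- After the randomization visit, PACC is first due at Month 6 (SAP 5.2.2), and that window opens on Day 166 (SAP 2.4, Table 1). No on-treatment PACC after baseline is scheduled for this subject.
- Carry-forward does not supply one. SAP 5.1.2 applies it only at on-treatment visits, and SAP 5.2.2 sets the composite to missing if more than one of its four components is imputed.
- SAP 5.2.1 requires at least one post-baseline change score. Within an on-treatment model this subject contributes nothing.
- The missing-at-random argument in SAP 5.2.3 relies partly on available efficacy scores. Here only baseline data are available.

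**4. What the off-treatment summaries give.** SAP 2.3 states: "For visit dates after the treatment end date, an Analysis Day is defined relative to the treatment end date", plus 1. For the same subject:
- Month 6 visit on Day 183: 183 − 80 + 1 = 104, which falls in the Month 3 window (82 to 106).
- Month 12 visit on Day 365: 365 − 80 + 1 = 286, which falls in the Month 9 window (257 to 288).

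Change is taken from the off-treatment baseline, which SAP 2.4 equates with the last on-treatment result after baseline. This subject has none. SAP 2.3 also refers to the last observation before last dose, which might let Day 1 serve. On either reading the summaries do not give a randomized comparison at Months 6, 12 and 18.

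**5. Scale, with assumed inputs.** Let pA and pP be the shares of an active arm and placebo that stop individually, and d the mean amount by which stoppers' later PACC differs from what the model predicts. With the same d in both arms, the on-treatment contrast misses (pA − pP) × d.

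| pA, pP (assumed) | d = −0.5 | d = −2 |
|---|---|---|
| 5%, 5% | 0 | 0 |
| 10%, 5% | −0.025 | −0.10 |
| 20%, 5% | −0.075 | −0.30 |
| 30%, 10% | −0.10 | −0.40 |

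If d differs by arm, the expression is pA·dA − pP·dP, and equal rates need not cancel.

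For precision, 557 − 447 = 110 subjects had more than 12 months of treatment, about 37 per arm. With the Month 36 SD of 2.44 (SAP 1.4), the standard error of a difference is 2.44 × √(2/36.7) = 0.57. If all 557 contributed, about 186 per arm, it would be 2.44 × √(2/186) = 0.25. The SD at Months 6 to 18 is not given and may be smaller.

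**The case against.** The strongest reply is that the SAP conceals nothing. It says the objectives cannot be evaluated (Section 1), that no formal hypothesis testing will be done (1.3), that comparisons are exploratory (5.1.1) and that no estimand is specified (5.2.1). The protocol's estimand is at Month 54, and no subject had more than 27 months of treatment. A reader might infer that the SAP breaches Protocol 11.3.1; the documents do not support this, because the estimand was openly withdrawn once it could not be reached. Nor is the model passed off as something else: intent-to-treat names the subject set, and the data rule is called on-treatment wherever it appears.

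A reader might also infer that the result is biased, and in which direction. That is not supported either. Arm-related stopping does not by itself violate missing at random, since treatment and its interaction with time are in the model, and the liver rules are triggered by enzymes, not cognition. If the assumption holds, the model validly estimates a hypothetical on-drug effect. The liver evidence in Protocol 1.4 (11 subjects above 3 times the upper limit: 9 active, 1 placebo, 1 blinded) pools several studies and gives no denominators by arm. The SAP does report reasons for discontinuation by group (4.2) and off-treatment PACC changes (5.2.3).

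All of this stands and lowers the weight of the point. It does not remove it. The model is still called the primary analysis and yields differences, confidence intervals and p-values at the 0.05 level. The off-treatment summaries are re-timed and re-baselined, and no analysis replaces the sensitivity work foreseen in Protocol 11.3.4.

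**Conclusion.** The point holds as a cheap improvement to an exploratory analysis. The only inferential PACC composite model is conditional on staying on drug. It leaves out scores that the protocol meant to include, and subjects who stop in the first 3 months would normally drop out of it altogether.

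Its size and direction are unknown. The illustrative gaps run from 0 to 0.40 PACC units and rest wholly on assumed stopping rates and differences; the standard errors of about 0.25 to 0.57 rest on a Month 36 SD. It is tempting to express such a gap as a share of the planned difference of 0.49. The documents do not support that, because 0.49 is a Month 54 planning value and the contrasts are at Months 6 to 18.

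A reader might also conclude that Protocol 11.3.1 should lose its exclusion of scores after clearly unrelated stops. That rule was added in Amendment 5 together with the estimand definition, and rewording it in a stopped trial would change nothing. The conclusion here assumes that at least some subjects stopped individually before 17 May 2018 and had PACC measured afterwards. The protocol asks for those visits, but the documents do not report the numbers.

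**What to change.** In SAP 5.2.3, add an MMRM for Months 6, 12 and 18 with the same fixed terms, specified as follows:
- **Scores:** all PACC scores collected up to 17 May 2018, including those after individual discontinuations; at minimum those after stops potentially related to treatment, as in Protocol 11.3.1.
- **Timing:** visits windowed from first dose, whether on or off drug.
- **Baseline:** change from the randomization baseline, not the off-treatment baseline.
- **Imputation:** one component rule on and off drug, in place of the present carry-forward on treatment and none off treatment (SAP 5.1.2 and 5.2.2).
- **Sponsor-wide stop:** administrative censoring at 17 May 2018.

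Keep the present model. In SAP 5.2.1, describe it as an on-treatment analysis of randomized subjects with at least one on-treatment post-baseline PACC. Present both models beside the discontinuation reasons by arm already planned in SAP 4.2.

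The cost is re-windowing, re-deriving change scores and some programming, with no new data collection. Off-drug scores may dilute a pharmacological effect, which is why the on-treatment model should stay.

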5.2.2. Definition

The primary endpoint is the PACC change score.

The PACC change score at a time point is a composite of 4 standardized changes from baseline (two episodic memory tests, one timed executive function test, and a test of global cognition) at that time point as follows:

PACC change score = $Z1+Z2+Z3+Z4$, where

- $Z1 = (\text{change from baseline in FCSRT score} / \text{SD of the baseline FCSRT score})$, where the FCRST score is twice the number of correct free recalls in 3 trials plus the number of correct cued recalls in 3 trials from the Free and Cued Selective Reminding Test (FCSRT). See Section 5.4.1.1 for details of the FCSRT.
- $Z2 = (\text{change from baseline in WMS test score} / \text{SD of the baseline WMS test score})$, where the WMS test score is the total number of correct recalls after a 30-minute delay from the Wechsler Memory Scale (WMS) Logical Memory subtest (delayed paragraph recall). See Section 5.4.1.2 for details of the WMS Logical Memory subtest.
- $Z3 = (\text{change from baseline in DSS test score} / \text{SD of the baseline DSS test score})$, where the DSS test score is the number of correctly drawn symbols completed in 120 seconds from the Wechsler Adult Intelligence Scale (WAIS)-IV Coding subtest (also known as the Digit Symbol Substitution [DSS] test). See Section 5.4.1.3 for details of the WAIS-IV Coding subtest.
- $Z4 = (\text{change from baseline in MMSE total score} / \text{SD of the baseline MMSE total score})$, where the MMSE total score is the total number of correctly completed items on the Mini-Mental State Examination (MMSE). See Section 5.4.1.4 for details of the MMSE.

The PACC baseline score is the sum of the 4 components' standardized baseline value (baseline value / SD of baseline values). The PACC scores will be considered missing if more than 1 of its 4 components is imputed (see Section 5.1.2). Change from the off-treatment baseline (see Section 2.4) will be calculated. For off-treatment visits, however, the components will not be imputed. The PACC scores will be considered missing if any of the components is missing.

The scales contributing to the PACC all follow the same schedule: during screening, at the randomization visit, and every 6 months after randomization through Month 54 (or early termination).

5.2.3. Analysis Methods

The primary analysis is based on the primary analysis set defined in Section 5.2.1 and uses an MMRM model. This relies on the Missing at Random (MAR) assumption: after accounting in the model for the effects of the covariates and for the available efficacy scores, the unobserved data have the same distribution as the observed data.

The PACC change score will be analyzed by an MMRM model based on observed data at on-treatment visits. The fixed terms for this model are treatment group, sex, country, APOE ε4 carrier status, education level, PACC baseline score, age at study entry, average hippocampal volume at baseline, time point (as a factor), and the interaction of treatment and time point. Subject is included as a random effect.

Comparisons between each atabecestat dose group and placebo will be performed at Months 6, 12, and 18 by using the appropriate contrasts based on this model. The Kenward-Roger approximation will be used to estimate the denominator degrees of freedom. Between-treatment differences in LS Means with the corresponding 95% confidence intervals (CIs) and p-values will be provided. If the unstructured covariance matrix results in a lack of convergence, starting values will be supplied using estimates from simpler structures. If this strategy does not result in

convergence then the following structures will be used in sequence: heterogeneous autoregressive of order 1 (ARH(1)), heterogeneous compound symmetry (CSH), and homogeneous compound symmetry (CS).

Plots of mean (\pm SE) PACC change score over time by treatment group will be provided for observed data and for estimates based on the MMRM.

For the off-treatment period, change of PACC and the components from off-treatment baseline will be summarized.

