### Screening Phase

The screening phase consists of 4 primary screening steps as shown below. In addition, part of the baseline cognitive, functional, and medical resource utilization/health outcomes measures will be performed during the screening phase, as described further below. Assessments for **Step III** (MRI) and **Step IV** (Elevated Amyloid Accumulation) may only be performed after the subject is determined to be still eligible for the study after review of results from **Step I** (General Health) and **Step II** (Clinical Scales). **Step III** must be completed before **Step IV**. The investigator must review the MRI results before the subject undergoes amyloid testing. The specific assessments and procedures to be performed during the screening phase are detailed on the Time and Events Schedule-Screening Phase.

\* PACC baseline assessment will be performed on Day 1 predose.

AD=Alzheimer's disease; CDR=Clinical Dementia Rating; CSF=cerebrospinal fluid; ECG=electrocardiogram; Min=minimum; MRI=magnetic resonance imaging; NAB-DLT=Neuropsychological Assessment Battery-Daily Living Test; PACC=Preclinical Alzheimer Cognitive Composite; PET=positron emission tomography; RBANS=Repeatable Battery for the Assessment of Neuropsychological Status.

Evidence of the subject's general health will be assessed in screening **Step I**, while confirmation of the subject's asymptomatic clinical status at baseline, as shown by a CDR global score of 0, will be obtained in screening **Step II**. A practice session with each of the cognitive performance scales (PACC, RBANS, NAB-DLTs for Memory and Attention, and the computerized cognitive battery) will occur during the screening phase and must be completed (1) prior to **Step IV** assessments, and (2) no later than 20 days (ie, Day -20) before the start of dosing. The subject's baseline functional performance will be profiled during screening by means of the CFI, CFI-a, ADCS-ADL-PI, and A-IADL-Q (informant [selected sites only]).

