## Footnotes:

- a Screening assessments may be performed over multiple visits over a period of 90 days prior to dosing, with the determination of inclusion and exclusion criteria occurring over Visits 1 through 5. If needed for biomarker collection or interpretation, or for logistical reasons, this period can be prolonged with written approval from the sponsor. Steps III and IV assessments may only be performed after Steps I and II assessments relevant for determination of eligibility are done and if, based on the results, the subject is eligible for continued participation. The order of individual assessments within a step is not fixed, unless indicated otherwise. Different screening assessments associated with each step may be performed on a single visit day or spread over multiple visit days. Eligible subjects based on Steps I to IV assessments will return during the screening phase to the site to have part of their baseline cognitive and functional measures performed between Day -10 and Day -5 and at least 2 days post amyloid disclosure. Although visit numbers are specified, fewer or additional visits can occur based on the above, and the numbering is considered guidance.
- b This visit will be performed once Step IV results are available and must take place at least 2 days prior to the baseline cognitive assessments.
- c The Informant should sign an ICF or equivalent document prior to completing any informant related study procedures.
- d Dermatological examination performed by a dermatologist (as defined in Section 9.1.2) with photography (taken by dermatologist or qualified designee) it is preferred that the dermatology exam be conducted before Step III, but it must be conducted before amyloid testing
- e The Assessment of Psychological Well Being will consist of the State-Trait Anxiety Inventory only at screening, as the GDS short version will be extracted from the GDS.
- f Including coagulation, vitamin B12, and folic acid.
- g Only for those subjects having a PET scan performed to assess eligibility.
- h Administered by phone (or at a visit) within 3 days post amyloid disclosure visit.
- i In order to assess for and mitigate practice effects, the PACC, RBANS, NAB-DLTs for Memory and Attention, and computerized cognitive battery must be performed once during the screening period but (1) prior to Step IV assessments, (2) no later than Day -20.

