that the subject is willing to receive a report of a pathological biomarker result and that, in the judgment of the investigator, the disclosure would not constitute a significant risk for the subject. As discussed below, these same questionnaires are also to be completed following disclosure of the subject's amyloid status in Step IV.

Subjects will have a single practice session during the screening phase for the PACC, RBANS, NAB-DLTs for Memory and Attention, and computerized cognitive battery. These practice sessions will be done to assess and mitigate potential practice effects. Practice sessions can occur at any time during screening but must be completed (1) prior to Step IV assessments, and (2) no later than 20 days (ie, Day -20) before the start of dosing.

**Evidence of any brain disease (Step III), other than potential very early clinical signs of AD** (eg, mild hippocampal atrophy) or typical age-related changes (eg, mild white matter hyperintensity on MRI), will be assessed during screening by means of cerebral MRI. Screening MRI results that demonstrate any relevant other pathology that by itself is likely to result in decline of cognitive function are exclusionary (see Section 4.2). Central and local review of the MRI will be performed, and where discrepancies are noted, the central read will be viewed as the primary source of information for eligibility determination in consultation with the sponsor's medical monitor.

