Slight differences in the PACC, version used in this study, from the ADCS-PACC include changes to some of the figures and text of the FCSRT to facilitate cultural adaptation and translations to other languages, inclusion of a different Logical Memory paragraph for administration during screening, and use of serial sevens in the MMSE instead of spelling “world” backwards.

Each component score will be transformed into z-scores. These z-scores will then be summed to form the composite. A decrease of 1 baseline standard deviation (SD) on each component would result in a 4-point decrease in the composite.

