1. INTRODUCTION

This statistical analysis plan (SAP) contains definitions of analysis populations, derived variables and statistical methods for the analysis of efficacy and safety for study 54861911ALZ2003.

Screening, randomization, and dosing in this study was stopped on 17 May 2018. Randomized subjects were to continue in the double-blind treatment phase without treatment (as allowed by protocol) for approximately 3 to 6 months from cessation of dosing. This permitted continued safety monitoring of the subjects per protocol. The planned last-patient-out date is 17 September 2018, except for some subjects who may require further follow-up.

At the time of cessation of screening and randomization, 557 (34%) subjects of the planned 1650 had been randomized. The planned duration of treatment was 54 months. As of the time of cessation of dosing, no subject had more than 27 months of treatment and 447 had 12 months of treatment or less.

As a result of the significantly reduced sample size, the objectives of the study as stated in the protocol and in Section 1.1 below cannot be evaluated. Safety outcomes will be summarized with descriptive statistics. The planned interim analysis of CSF A β ₁₋₄₀ was performed but other planned interim analyses will not be performed. Between-group comparisons of selected efficacy outcomes will be performed. Other efficacy outcomes will be summarized with descriptive statistics

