2.4. Visit Windows

As subjects do not always adhere to the protocol visit schedule, the following rules are applied to assign actual visits to analysis visits. Listed below are the visit windows and the target days for each visit. The same definitions will apply to visits before or after the treatment end date using the Analysis Day as defined in Section 2.3 above. The time period description will be appended with '(On-Trt)' for post-baseline visits on or prior to the treatment end date. The time period description will be appended with '(Off-Trt)' for post-baseline visits after the treatment end date. If a subject has 2 or more actual visits in one visit window, the visit closest to the target day will be used as the protocol visit for that visit window. The other additional visit(s) will not be used in the summaries or analyses but they can be used for determination of clinically important endpoints. If 2 actual visits are equidistant from the target day within a visit window, the later visit will be used.

All assignments will be made in chronological order. Once a visit date is assigned to a visit window, it will no longer be used for a later time point except for the endpoint. Listed below (Table 1) are the visit windows and the target days for each visit defined in the protocol.

Table 1: Visit Windows for on and off-treatment Analysis

Scheduled Visit Number	Time period (label on output)	Time Interval (Day*)	Target Time Point (Day)
7	Baseline	-120 to 1	1
8	Week 2	2 to 22	15
9	Week 4	23 to 36	29
10	Week 6	37 to 50	43
11	Week 8	51 to 64	57
12	Week 10	65 to 81	71
13	Month 3	82 to 106	92
14	Month 4	107 to 134	120
15	Month 5	135 to 165	148
16	Month 6	166 to 211	183
17	Month 8	212 to 256	239
18	Month 9	257 to 288	274
19	Month 10	289 to 333	302
20	Month 12	334 to 410	365
21	Month 15	411 to 501	456
22	Month 18	502 to 592	547
23	Month 21	593 to 683	638
24	Month 24	684 to 774	729
25	Month 27	775 to 865	820
26	Month 30	866 to 956	911
27	Month 33	957 to 1047	1002
28	Month 36	1048 to 1138	1093
29	Month 39	1139 to 1229	1184
30	Month 42	1230 to 1320	1275
31	Month 45	1321 to 1411	1366
32	Month 48	1412 to 1502	1457
33	Month 51	1503 to 1593	1548
34	Month 54	1594 to 1684	1639
	Month >54	1685 to ∞	1685

* Relative to analysis reference start date if visit date is prior to or on the treatment end date. Relative to treatment end date if visit date is after treatment end date.

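### A second pre-dose PACC score is collected but left out of the primary MMRM: the model is valid, but it forgoes a modest precision gain that the documents cannot size

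*SAP*

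**What the plan says.** **Two pre-dose scores.** SAP 5.2.2: "The scales contributing to the PACC all follow the same schedule: during screening, at the randomization visit, and every 6 months after randomization". Protocol 9.1.2 describes the first administration: "Subjects will have a single practice session during the screening phase for the PACC, RBANS, NAB-DLTs for Memory and Attention", among others. It must precede Step IV and fall no later than Day -20. A footnote to the screening Time and Events Schedule gives the purpose: "In order to assess for and mitigate practice effects". The second is the reference: "PACC baseline assessment will be performed on Day 1 predose" (Protocol synopsis, Screening Phase). The RBANS is also given twice (SAP 5.4.1.8): at screening before amyloid testing, and again 5 to 10 days before randomisation, the latter being its baseline.

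**One score in the model.** The MMRM in SAP 5.2.3 has treatment, sex, country and APOE ε4 status, then "education level, PACC baseline score, age at study entry, average hippocampal volume at baseline, time point (as a factor", and the treatment-by-time interaction. There is one PACC term. SAP 5.4.2 uses a similar model for the RBANS indices and Total Scale, with the baseline of the endpoint concerned.

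**The other score is set aside.** SAP 2.4 defines the baseline window as Day -120 to 1 with target Day 1 and keeps the closest visit: "The other additional visit(s) will not be used in the summaries or analyses", except for determining clinically important endpoints.

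**Size and status.** SAP 1: "557 (34%) subjects of the planned 1650 had been randomized", and 447 of them had 12 months of treatment or less. Contrasts with confidence intervals and p-values are still planned at Months 6, 12 and 18. SAP 5.1.1 calls all comparisons exploratory.

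**The concern.** The screening PACC is a second measurement of the outcome itself, taken before randomisation. Day 1 alone carries test-retest error. A second score averages some of that out and so explains more of the variation in later scores. The model already spends terms on age, sex, education, country, APOE ε4 status and hippocampal volume, so a repeat of the outcome is a natural addition. With about a third of the planned sample, the width of the intervals is the main limit on what the PACC contrasts can show. No section of either document enters the screening score in a primary or supportive model.

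**Working it through.** **1. The plan's own figures.** 557/1,650 = 33.8%, or 557/3 ≈ 186 per arm. Subjects with more than 12 months of treatment: 557 − 447 = 110, about 37 per arm. The stated 83% power (difference 0.49, SD 2.44, two-sided 0.05) is not a completers-only result: 385 per arm in a two-sample comparison gives 79.6%. It does reproduce under an MMRM with 550 per arm, constant correlation 0.5, linear attrition to 30% and dropouts contributing partial data: 83.1% to 84.3% with five or nine post-baseline visits.

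**2. Formula.** Let r be the correlation of raw Day 1 PACC with follow-up, take the screening-to-Day 1 correlation as r too, and let b be the correlation of screening with follow-up. Day 1 alone leaves residual variance proportional to 1 − r². Adding the screening score removes a further share of

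(b − r²)² / (1 − r²)².

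If b = r this simplifies to r²/(1 + r)². A simulation at r = b = 0.7 (186 per arm, 4,000 runs) gave a variance ratio of 0.838 against 0.830 by formula.

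**3. Range for r (assumed).** The documents give no PACC correlation between raw scores. The 0.5 in the sample size section does not supply one, because change scores correlate 0.5 under any compound-symmetric raw scores. A value can be back-solved from the change SD of 2.44, assuming equal variance s² at baseline and follow-up: 2.44² = 2s²(1 − r). The composite is a sum of four scores each scaled to unit baseline SD, so s² = 4 + 12c for inter-component correlation c. Taking c = 0.2 to 0.4 (assumed):

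- c = 0.2: s² = 6.4, r = 1 − 5.954/12.8 = 0.535
- c = 0.4: s² = 8.8, r = 1 − 5.954/17.6 = 0.662

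**4. Variance reduction over that range.**

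| Screening-to-follow-up correlation b | r = 0.535 | r = 0.662 | Narrowing of CI |
|---|---|---|---|
| equal to r | 12% | 16% | 6% to 8% |
| r − 0.10 | 4% | 5% | about 2% |
| r − 0.15 | 2% | 2% | about 1% |
| r² | 0% | 0% | none |

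The top row equals 14% to 19% more subjects (1/0.879 and 1/0.841). The 2.44 is a Month 36 figure from an external cohort, while the contrasts are at Months 6, 12 and 18, so r could lie outside this range in either direction. At r = b = 0.9 the formula gives 22%.

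**5. Other covariates.** If they explain 10% to 30% of the variance, the equal-correlation reduction falls from 11% to between 10% and 5% at r = 0.5, and from 17% to between 16% and 13% at r = 0.7.

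**6. Effect on power.** Take r = 0.6 and 186 per arm. Then s² = 5.954/0.8 = 7.44, and the residual SD with Day 1 alone is √(7.44 × 0.64) = 2.18. Power for 0.49 is 58%. It becomes 65% if b = r (residual SD 2.02) and 60% if b = 0.5. The difference detectable with 80% power moves from 0.63 to 0.59 in the better case. At 37 per arm and SD 2.44, the unadjusted 95% half-width is 1.96 × 2.44 × √(2/37) = 1.11. It becomes 1.02 to 1.04 in the top row of the table, and power for 0.49 goes from about 14% to about 15%.

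**The case against.** The strongest reply is that nothing here is wrong. The covariates match the list in Protocol 11.3.1, the amended SAP specifies no primary estimand and no formal testing, and development has ended on hepatic safety grounds. The screening PACC may also be a poor predictor. It is a first-exposure practice run, with "inclusion of a different Logical Memory paragraph for administration during screening" (Protocol 9.2.1). It precedes amyloid disclosure and can fall up to 90 days before dosing, or earlier with sponsor approval. All of this could lower b, and the table shows how quickly the gain then vanishes.

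Much of that stands: the weight is limited and the size is unknown. It does not argue against the change. A mean practice gain goes into the intercept; only a loss of correlation matters. Protocol 9.2.1 calls the three alternate forms, including the one used at screening, functionally and psychometrically equivalent. The score precedes randomisation, so adjusting for it cannot bias the contrast. The documents explain why screening is not the baseline, but not why it could not be a covariate.

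The reply is also right that editing 5.2.3 alone is not enough. SAP 2.4 would still bar the value, and a missing covariate would drop the subject from a standard MMRM.

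**Conclusion.** The point holds as a missed gain in precision. Under the assumptions above, the variance of the PACC contrast would fall by about 0% to 16%, or 0% to 8% off the width of the intervals, before the other covariates take their share. The size for the RBANS models was not calculated.

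Three stronger readings are tempting, and the documents support none of them:

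- **That the model is biased or misspecified.** It adjusts for the outcome's own baseline and the prespecified covariates, and is valid.
- **That a gain of 12% to 16% is established.** That figure needs the screening score to predict follow-up as well as Day 1 does, and neither document gives that correlation.
- **That the change would rescue the comparison.** Power for 0.49 stays well below 80% with all 186 per arm, and Month 18 stays uninformative.

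The point does not extend to the NAB-DLTs, although they share the practice session: SAP 5.4.2 specifies no MMRM for them.

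**What to change.** Before unblinding:

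- **SAP 5.2.3:** add the screening PACC score, standardised by the same baseline SDs, as a fixed covariate beside the Day 1 PACC score.
- **SAP 5.4.2:** add the corresponding screening RBANS score to the RBANS models.
- **Reference for change:** leave it as it is, Day 1 for the PACC and the Day -10 to -5 assessment for the RBANS.
- **Re-screened subjects:** use the latest screening score.
- **SAP 2.4:** state an exception so that the screening value may serve as a covariate.
- **Missing or partial screening scores:** impute from pre-randomisation data only, for example the overall mean or a regression on the baseline score, so that no subject is dropped.

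The cost is one degree of freedom per model and a small amount of extra derivation. No new data are needed.
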